COVER PAGE

Official Study Title: Feasibility of Blood-flow Restriction Training Prehabilitation in Older Adults Awaiting Total Knee Replacement

NCT number: NCT06111690

IRB Approval Date: 09-05-2024

Unique Protocol ID: HSC20210590H

Protocol Template Form

Item 1 UTHSCSA Tracking Number	HSC20210590H
---	--------------

Item 2 Abstract / Project Summary	Provide a succinct and accurate description of the proposed research. State the purpose/aims. Describe concisely the research design and methods for achieving the stated goals. This section should be understandable to all members of the IRB, scientific and non-scientific. DO NOT EXCEED THE SPACE PROVIDED.
--	--

Purpose/Objectives: The overall aim of this research is to demonstrate that preoperative exercises (prehabilitation) using blood-flow restriction training (BFRT) is safe, well tolerated, improves muscle function, decreases functional limitation, and increases physical activity in older adults awaiting total knee replacement (TKR).

Research Design/Plan: This is a single group pre-post design study. Outcomes will be measured at baseline, after 6 weeks of prehabilitation, and 8 weeks after TKR.

Methods: Twenty individuals ≥ 60 years old awaiting TKR due to diagnosis of end-stage knee osteoarthritis who meet the inclusion/exclusion criteria will be invited to participate in a 6 weeks of low-intensity BFRT prehabilitation. We will assess muscle morphology (i.e., cross-sectional area and intramuscular fatty content) using dual x-ray absorptiometry (DEXA) scan, quadriceps muscle strength using an isokinetic dynamometer, a battery of performance-based physical function, self-reported physical function and quality of life, and biomarkers of inflammation using blood serum. Feasibility assessment will be done by looking at safety (i.e., adverse events), compliance, and attrition rate.

Clinical Relevance: The low intensity prehabilitation program using BFRT may lead to improvements in muscle morphology and strength, as well as physical function before TKR. Since muscle weakness and functional limitations experienced preoperatively affect the recovery after TKR, these individuals may experience a significant benefit from our program. Thus, our program may allow patients undergoing TKR to perform daily activities early on postoperatively. Moreover, by increasing physical activity and preventing exacerbation of joint inflammation, our program might impact the general health in older adults after TKR.

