
Item 4
 
Purpose and rationale
 
Insert purpose, objectives and research questions/hypotheses here.
 
If you cut and paste from another document, make sure the excerpted material answers the question
	
Primary outcome: feasibility of BFRT during prehabilitation in older adults awaiting TKR.
 
Secondary outcomes: muscle strength and morphology (i.e., volume and quality), physical function, real-time physical activity and concentration of inflammatory biomarkers.
 
Endpoint: Baseline (T0), after 6 weeks of prehabilitation (T1) and 8 weeks postoperative (T2)
 
Justification for Endpoint: - T0 will provide overall idea on subjects' baseline characteristics of outcome-related data.
 
- T1 will provide data on safety, compliance and attrition rate of the BFRT prehabilitation program, as well as its effect on muscle strength and morphology, physical function, real-time physical activity and concentration of inflammatory biomarkers.
 
- T2 will provide data on the continuing effect of BFRT prehabilitation on muscle strength and morphology, physical function, real-time physical activity and concentration of inflammatory biomarkers postoperatively.
 
Rationale: The low intensity prehabilitation program using BFRT may lead to improvements in muscle morphology and strength, as well as physical function before TKR. Since muscle weakness and functional limitations experienced preoperatively affect the recovery after TKR, this population may experience a significant benefit from our program. Thus, the results of our investigations may allow patients undergoing TKR to perform daily activities early on postoperatively. Moreover, by increasing physical activity and preventing exacerbation of joint inflammation, our program might impact the general health in individuals after TKR.

Item 5 Study Population(s) Being Recruited
 
In your recruitment plan, how many different populations of prospective subjects do you plan to target? Provide number: 1
	
Identify the criteria for inclusion:
	
---	--	--

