
Older adults with knee osteoarthritis awaiting total knee replacement
	
Individuals will be included if they: (a) are awaiting primary unilateral TKR due to diagnosis of end-stage KOA. Potential individuals must have at least 8 weeks waiting time in between study baseline assessment and surgery. This 8-week timeframe will allow for completion of baseline (T0) and follow-up assessments (T1: immediately after 6-week prehabilitation program); (b) are older than 60 years; (c) speak fluent English to reliably complete the study questionnaires and understand study instructions.
	
To ensure safety, Individuals will be excluded from the study if they: (a) have a history of cardiovascular disease, uncontrolled hypertension (blood pressure $\geq 140/90$ mmHg), deep-vein thrombosis, varicose veins, or rhabdomyolysis; (b) have absolute contraindications to exercise, as established by the American College of Sports Medicine (uncontrolled arrhythmias, third degree heart block, recent EKG changes, unstable angina, acute myocardial infarction, and acute congestive heart failure); (c) report of 2 or more falls within the past year; (d) cannot walk a distance of 100 feet (30.5 meters) without an assistive device or need of a rest period; (e) have bilateral TKR or undergoing TKR revision or other total joint replacement in the lower extremities; or (f) have severe visual or hearing impairment. In addition to the affects that these impairments have on safety during participation in the intervention, they may also interfere with data collection (questionnaires and telephone checks); (g) have a lower extremity amputation; (h) are unable to comfortably bear weight on the affected knee; (i) have a BMI above 40. This exclusion is used because subjects with BMI ≥ 40 are more likely to develop patellar radiolucencies, have poorer muscle function and more pain.
 
To minimize potential confounding effects, individuals will be excluded if they have: (j) history of muscular disease (e.g., muscular dystrophy) or neurological disorder that may affect lower extremity function (e.g., cerebrovascular accident, neuropathy, Parkinson's disease, multiple sclerosis); (k) had additional surgery to the lower extremities within the past 12 months.

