Primary Outcomes: 1) Quadriceps muscle function:

1a. Strength will be measured using an isokinetic dynamometer (Biodex System 4 Pro, Shirley, NY). We will record the quadriceps femoris maximum voluntary isometric contraction (MVIC) as torque output (Nm). Subjects will be seated in the dynamometer's chair with their knee at 60 degrees of flexion. Subject position, stabilization, and gravity correction will be performed according with the Biodex manufacturer's guidelines. Subjects will exert as much isometric force as possible while trying to extend the knee against the force arm of the dynamometer. The MVIC will be the highest torque (Nm) of four trials.³³ Torque will be the variable used in data analysis. Strong verbal encouragement from the tester and visual feedback from the dynamometer screen will be provided during trials. Previous studies using this method in individuals with arthritis indicate that it was tolerated well and did not result in adverse effects.^{34,35}

1b. Cross-sectional area and Quality will be measured using a whole-body DEXA scan to investigate muscle composition of the thigh region bilaterally.^{36,37} Serial axial plane DEXA scan will be used to quantify changes in thigh muscles cross sectional area (CSA) and quality (i.e., amount of intramuscular fat) bilaterally. Subjects will be imaged in supine with the legs extended flat on the table. The scanner measures the absorption of two different energy levels of X-rays as they pass through the body. This information is used to create an image of the body that shows the distribution of bone, fat, and muscle tissue that have different X-ray attenuation. Using these differences in X-ray attenuation, the DEXA software is able to distinguish and quantify the amount of muscle and fat in a specific region of interest, such as the thigh muscles.

Secondary Outcomes:

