biomarkers. The laboratory will use the 'MILLIPLEX® MAP Human High Sensitivity T Cell Magnetic Bead Panel' to assess a panel of 8 inflammatory biomarkers: Interleukin (IL)-1 β , IL-2, IL-5, IL-6, IL-10, IL-12p70, IL-13 and Interferon- γ .^{32,53}

Additional Measures

1) Demographic factors: age, gender, ethnicity, marital and educational status

2) Biomedical factors

a) Medication prescribed and over-the-counter used for pain will be recorded in the medication form. We will record the current and highest dosage of any pain medication used during the last month (when performing pre-intervention evaluation), or during the interval between evaluations.

b) Comorbidity data will be collected using the Cumulative Illness Rating Scale.⁵⁴

c) Body Mass Index will be calculated as the subject's body weight divided by the height squared.

d) Knee Range of Motion will be measured in the supine position utilizing a standard goniometer. The available range of knee flexion and extension will be measured. When measuring passive knee extension, the heel will be elevated on a bolster to ensure the end range of extension is achieved.

e) Knee Pain in both knees (surgical and non-surgical sides) will be measured using an 11-point (0 to 10) numeric scale. The scale will be anchored at one end with the phrase "no pain" (0) and at the other end with the phrase "worst imaginable pain". Subject will be instructed to report the greatest pain during last 24h.^{55,56}

Research personnel will keep track of assessment procedures using a checklist. An exercise log will be used to track delivered exercise sessions. All questionnaires will be self-administered using Redcap.

Although subjects are asked to not participate in any exercise-related program during the study period, research personnel will track exercises performed by subjects on a log.

Study personnel reserve the rights to discontinue delivery of intervention if subject presents with muscle or joint pain that cannot be resolved by administering over-the-counter pain medication.

Research personnel will ensure to follow-up with subjects who have discontinued the study in regards to their recovery from muscle or joint flare-ups due to study intervention to monitor AE, SAE and/or UPIRSOs.

Statistical Considerations

Statistical Hypotheses

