State the formal and testable null and alternative hypotheses for primary and key secondary endpoints, specifying the type of comparison (e.g., superiority, equivalence or non-inferiority, dose response) and time period for which each endpoint will be analyzed.

Our hypotheses are that:

- our exercise protocol will be safe, compliance with intervention will be >80% of completed exercise sessions, and retention will be >80% of subjects.

- Subjects will demonstrate improvement in muscle strength and morphology, physical function, quality of life, physical activity, and biomarkers of inflammation from T0-T1 (before TKR), which will hold true from T0-T2 (after TKR).

Sample Size Determination

Include number of participants to recruit, screen, and enroll to have adequate power to test the key hypotheses for the study. Provide all information needed to validate your calculations and judge the feasibility of enrolling and following the necessary number of participants.

Due to the exploratory (pilot) nature of the study, we aim to recruit 20 subjects to answer our question on the feasibility of our exercise protocol.

Populations for Analyses

Clearly identify and describe the analysis datasets (e.g., which participants will be included in each).

This is a single group pre-post design. All participants recruited will be assessed regarding compliance, adherence, and safety of our exercise protocol. Data on demographics, biomedical factors, and outcomes measures (i.e., muscle

strength and morphology, physical function, quality of life, physical activity, and biomarkers of inflammation) will be entered in the dataset for each timepoint.

Statistical Analyses

Include analysis of primary efficacy endpoints, secondary endpoints, safety analyses, and any planned interim analyses. Descriptive statistics on adverse events (i.e., joint and/or muscle pain) during exercise sessions and at each timepoint will be provided. Data on secondary outcomes (i.e., muscle strength and morphology, physical function, quality of life, physical activity, and biomarkers of inflammation) will be compared between T0-T1, T0-T2 and T1-T2.

Due to the small sample size (N=20) we will conduct a non-parametric paired difference test (i.e., Wilcoxon signed-rank test) to identify whether those comparisons are statically significant.

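### The only planned safety analysis summarises joint and muscle pain alone, so vascular, cuff-related and other non-pain events would fall outside the summary supporting the safety hypothesis

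*Combined protocol and SAP*

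**What the plan says.** Item 4 gives "Primary outcome: feasibility of BFRT during prehabilitation in older adults awaiting TKR", and the abstract (Item 2) adds: "Feasibility assessment will be done by looking at safety (i.e., adverse events), compliance, and attrition rate". Under Statistical Hypotheses in Item 6 the feasibility hypothesis is that "our exercise protocol will be safe, compliance with intervention will be >80% of completed exercise sessions, and retention will be >80% of subjects". Compliance and retention each carry a threshold; safety carries none.

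The analysis is one sentence under Statistical Analyses: "Descriptive statistics on adverse events (i.e., joint and/or muscle pain) during exercise sessions and at each timepoint will be provided". The Data Analysis Plan that follows covers the flow chart, dropout and outcome summaries, and adds no further safety analysis.

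Collection is described more broadly. The visit procedures provide for adverse event monitoring at every visit. Additional Measures has staff follow up participants who stop, to "monitor AE, SAE and/or UPIRSOs", although that sentence is about recovery from muscle or joint flare-ups. The session log described under Step-by-Step Methods records exercise completion and pain in both knees before, during and after each session.

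Item 5 excludes, on safety grounds, people with a history that includes cardiovascular disease and "deep-vein thrombosis, varicose veins, or rhabdomyolysis". It also lists sickle cell disease and cuff placement on a limb with lymphedema or vascular access. Screening in Item 6 adds an ankle-brachial index to rule out arterial disease.

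**The concern.** Safety is one of the three stated components of feasibility, and this sentence is the only analysis that informs it. The intervention uses a cuff that blocks venous return during exercise, and the protocol screens out people with several vascular and muscle-breakdown conditions. The analysis nevertheless defines the events to be summarised as joint and/or muscle pain. A report that followed the plan exactly could describe pain, conclude that the protocol was safe, and leave out a recorded vascular event. A later, larger trial would then take its safety assumptions from an incomplete summary.

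**Working it through.** The plan gives no safety figure to reproduce: N=20 comes without an event rate, confidence level or power. The check is therefore mainly a comparison of texts.

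**1. Scope, place by place**

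| Place | Scope of safety |
|---|---|
| Item 2, Methods | Adverse events, no limit on type |
| Item 6, Study visit procedures | Adverse events at every visit, no limit on type |
| Item 6, Populations for Analyses | All recruited participants assessed for safety, no limit on type |
| Item 6, Additional Measures | AE, SAE and UPIRSO, in the setting of muscle or joint flare-ups |
| Item 6, Statistical Analyses | Joint and/or muscle pain |

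The analysis is narrower than the definition, the visit-level monitoring and the analysis population.

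**2. Tracing events through the plan**

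- Knee pain during a session: logged and summarised.
- A thrombosis or muscle breakdown that presents with leg pain: monitored, and possibly counted, but only as pain.
- A vascular, cuff-related or other event without pain: monitored at the visit, but with no place in the summary.

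Nothing elsewhere in the plan says how the last two would be tabulated by type.

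**3. Scale of what 20 participants can show (illustration only)**

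With no events among n participants, the exact two-sided 95% upper limit solves (1 − p)^n = 0.025, so p = 1 − 0.025^(1/n).

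- n = 20, the planned number: 1 − 0.025^(1/20) = 0.168, or 16.8%. The one-sided 95% limit is 1 − 0.05^(1/20) = 0.139, or 13.9%.
- n = 17, the smallest whole number above 80% retention of 20 (17/20 = 85%, whereas 16/20 is exactly 80%): 1 − 0.025^(1/17) = 0.195, or 19.5%.

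These limits follow from sample size and would be the same after the sentence is corrected. They do not measure the defect. They show why a safety conclusion should be given as a rate with its upper limit.

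**The case against.** The strongest reply is that i.e. is a slip for e.g. and that the sponsor intends to report every adverse event. The document's parenthetical lists are not reliably exhaustive: the outcome measures include morphology under Populations for Analyses, but the corresponding list in the Data Analysis Plan omits it. Against that, the document also uses i.e. to define terms, as in the abstract's explanation of safety and in naming the Wilcoxon test. Intent cannot be settled from the text. Either way the sentence needs correcting, because no other place says how non-pain events would be summarised.

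A reader might also infer the following, which the documents do not support:

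- **Other events go unmonitored.** The abstract and the visit procedures say otherwise. The gap is in the analysis.
- **Arthritis pain will inflate the safety table.** Pre-session pain is recorded, and nothing says it will be ignored. The plan simply does not say how it will be used.
- **The small sample is the fault here.** That 20 participants cannot exclude uncommon harms is a separate limitation of a declared pilot, and widening the table does not remove it.
- **The exclusions are a list of expected cuff harms.** Item 5 gives them under safety without tying each to restricted flow, and some are general contraindications to exercise. They show which kinds of event the protocol takes seriously, and no more.
- **Risks were not disclosed.** Item 7 refers to the consent document, which is not available here, so nothing can be concluded.

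**Conclusion.** The point stands as a mismatch of scope. The single planned safety analysis, followed as written, leaves non-pain events out of the summary supporting the safety hypothesis, although the protocol provides for monitoring them and treats some of their kinds as safety matters. Its size cannot be given as a number, because the documents state no event rates. It should be corrected before analysis.

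The conclusion rests on reading the parenthesis as a definition. If examples were meant, the remaining gap is that tabulation of other events is unspecified. It would overstate the matter to call this without qualification a flaw in the primary endpoint. Item 4 makes feasibility primary, but Item 6 has "Primary Outcomes: 1) Quadriceps muscle function", and the two must be reconciled. Safety belongs to the feasibility hypothesis under either label.

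**What to change.** Replace the sentence under Statistical Analyses with text to this effect:

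> All adverse events, SAEs and UPIRSOs recorded at any visit will be tabulated by type, with vascular and cuff-related events as one named category and joint or muscle pain as another. The number and percentage of participants with an event, with exact 95% confidence intervals, will be given separately for baseline to T1 and for T1 to T2. Events after surgery will be shown separately, because they cannot readily be attributed to the cuff.

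T1 and T2 here are as in Item 4 (after prehabilitation, and 8 weeks after surgery); the Data Analysis Plan numbers its timepoints differently. Starting at baseline keeps events from baseline testing in the table. State the denominator for each period.

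Summarise session knee pain as change from that session's pre-exercise score, which the log already holds. Replace the unquantified claim of safety in the hypothesis with observed rates and their upper limits. If the sponsor prefers a yes/no conclusion, it must define the criterion in advance.

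The cost is one more table and a more cautious safety statement; the sample size does not change. Tabulating severity and relatedness as well would be useful, but the documents describe neither, so those fields would have to be added to the adverse event record.

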Data Analysis Plan: A flow chart will be prepared to identify and summarize issues in recruitment and retention, record total numbers screened, numbers excluded with reasons for non-participation, timing and frequency of dropout, etc. Retention will be assessed by frequency count of dropouts. Survival analysis of time to dropout may point to parts of the protocol that are difficult (e.g., very early dropout, loss to follow-up).

We will perform a descriptive summarization of demographic and baseline (T1) values of biomedical factors, and outcomes measures (i.e., muscle strength, physical function, quality of life, physical activity, and biomarkers of inflammation), post 6-week prehabilitation values (T2), and 12 weeks (T3) after TKR values. Then, change values from T1 to T2, and change values from T1 to T3 will be described stratified by intervention group. This information will be important to perform formal sample size and power computations for a future larger trial. Due to the small sample size, more attention will be paid to a trend towards a relatively smaller p-value rather than statistical significance based on a strict criterion (e.g., $\alpha=0.05$).

Item 7 Risks Section:

Complete the following table to describe the risks of all **research procedures** listed in Step 2, Institutional Form (items 28-34). *Do not list risks of Routine care procedures here.*

☒ N/A, Risks are described in the informed consent document – do not complete this table.

Research procedures	Risks
example: 
 History and physical Questionnaire Laboratory tests 
Add or delete rows as needed
	
List the reasonably expected risks under the following categories as appropriate:

	○

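### Item 6 gives two conflicting rules for the secondary p-values, with no alpha, no definition of a trend and no intervals, so chance results among about 81 to 117 tests could be read as benefit

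*Combined protocol and SAP*

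**What the plan says.** All of this is in Item 6 of the combined protocol and SAP.

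- **Statistical Analyses.** Strength and morphology, physical function, quality of life, physical activity and inflammatory biomarkers "will be compared between T0-T1, T0-T2 and T1-T2". The test is the Wilcoxon signed-rank test, and its purpose is "to identify whether those comparisons are statically significant". No significance level or sidedness is given.
- **Data Analysis Plan.** Because the sample is small, "more attention will be paid to a trend towards a relatively smaller p-value rather than statistical significance based on a strict criterion". The value 0.05 appears only as an example of the criterion being set aside.
- **Data Analysis Plan, just before that sentence.** Summaries and change values are to be described, and "This information will be important to perform formal sample size and power computations for a future larger trial".
- **Sample Size Determination.** The study is called exploratory, and "we aim to recruit 20 subjects to answer our question on the feasibility of our exercise protocol".

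Neither section names a key secondary outcome or contrast, a multiplicity rule or a confidence interval. T0, T1 and T2 below are used as in Statistical Analyses (baseline, after prehabilitation, 8 weeks after surgery). The Data Analysis Plan numbers the occasions T1 to T3 and puts the last at 12 weeks, which needs reconciling separately.

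**The concern.** The two sections give different instructions for the same p-values. One sorts comparisons into significant and not significant without a level. The other shifts the emphasis to small p-values without saying how small. With no definition of a trend, almost any result could be given that name once the data are seen. The criterion is loosened exactly where there are few participants and many tests.

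This matters because Item 2 states the aim of demonstrating that the training improves function and activity, and Statistical Hypotheses predicts improvement in every outcome group. A scatter of small p-values would fit that expectation even if nothing had changed. A p-value also does not say how large a change is or what range of changes the data allow, and the plan specifies no interval that would.

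**Working it through.** The documents state no number of tests, power or error rate, and N=20 has no calculation behind it, so there is no planned figure to reproduce. The number of tests has to be built from the outcome descriptions.

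**Step 1. Outcome variables (Item 6)**

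| Outcome group | Low | Base | High |
|---|---|---|---|
| Quadriceps torque (high: each leg) | 1 | 1 | 2 |
| Thigh muscle area and fat (high: each thigh) | 2 | 2 | 4 |
| Performance tests | 4 | 6 | 8 |
| PROMIS (high: physical, mental, social) | 1 | 1 | 3 |
| RAND-36 scales | 8 | 8 | 8 |
| Actigraph (high: three intensity levels added) | 3 | 3 | 6 |
| Inflammatory biomarkers | 8 | 8 | 8 |
| **Total** | **27** | **29** | **39** |

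The performance row varies because the lists conflict. The visit schedule has six tests and Secondary Outcomes has four. Gait speed and stairs are common to both, so the merged list has 6 + 4 − 2 = 8.

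**Step 2. Tests.** Three contrasts per variable: 27 × 3 = 81, 29 × 3 = 87, 39 × 3 = 117.

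**Step 3. Expected chance results if nothing changed.** The expected count is the number of tests times the level, and correlation between tests does not alter it. Two-sided testing is assumed, so half the results fall in the favourable direction.

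- All 87 tests at 0.05: 87 × 0.05 = 4.35, of which 4.35 / 2 ≈ 2.2 favourable.
- All 87 tests at 0.10: 87 × 0.10 = 8.7.
- T0-T1 only, at 0.05: 29 × 0.05 = 1.45, of which about 0.7 favourable.
- Range at 0.05: 81 × 0.05 = 4.05 to 117 × 0.05 = 5.85.

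The exact signed-rank test is slightly conservative. With 20 pairs its attained two-sided level is 0.0484, so the 87 tests give 87 × 0.0484 ≈ 4.2.

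**Step 4. Chance of at least one result at p<0.05.** Unlike the expected count, this depends on correlation. With 87 independent tests it is 1 − 0.95^87 = 98.8%, an upper-end figure because the three contrasts share occasions. A simulation with no true change (29 outcomes, three occasions, 20 pairs, 4,000 runs) gave:

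| Correlation between outcomes | Any result | Any favourable result |
|---|---|---|
| 0 | 97% | 85% |
| 0.3 | 93% | 69% |
| 0.5 | 84% | 55% |
| 0.7 | 66% | 40% |

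With 16 pairs (80% of 20, the hypothesised retention threshold) the chance of any result runs from 97% down to 65%.

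**Step 5. Which contrasts speak to the training.** T0-T2 and T1-T2 both include the knee replacement, which accounts for 2 × 29 = 58 of the 87 tests. Item 3 itself credits the surgery with improving pain and quality of life. For those 58 the main difficulty is attribution. A genuine change there would still not be an effect of the training.

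**The case against.** The strongest defence is that this is a feasibility pilot. Feasibility is the primary outcome in Item 4 and the only reason given for 20 participants, so loose wording on secondary tests may do little harm. That holds for severity, since the feasibility results are untouched. It does not rescue the rule: exploratory status argues for estimates with their uncertainty, not for an undefined reading of p-values.

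Four stronger readings are tempting, and the documents do not support them.

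- *Chance findings will be reported as benefit, or will decide the next trial's outcomes.* No reporting rule or outcome-selection rule is stated. Given the stated aim and hypotheses, the results could be read that way, and no more can be said.
- *The Data Analysis Plan replaces the significance test.* It speaks of giving more attention, which is emphasis. The test in Statistical Analyses still stands, and the fault is the unresolved conflict between them.
- *P-values will feed the future sample-size calculation.* The sentence about planning follows the descriptive summaries and change values and refers to those. The p-value sentence comes after it. The gap is narrower: no SD of change is named and no interval is planned.
- *More than four false claims of benefit are to be expected.* Only about half of the 4.35 would be favourable, and a complete absence of change is implausible for many of the 58 tests that span surgery.

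The imprecision of an SD from 20 pairs is also no part of the fault. It follows from the sample size and would remain under any wording.

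**Conclusion.** The point holds as a conflict in the text with a measurable consequence. The two sections of Item 6 disagree on how p-values are used, no alpha is adopted, a trend is undefined, and neither multiplicity handling nor intervals are planned. In the base count, chance alone gives about 4.4 results at p<0.05 and 8.7 at p<0.10. Before surgery, where the training can be looked at without the operation, it gives about 1.5.

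These figures assume two-sided tests, no true change, and a count in which laterality, PROMIS scoring and Actigraph variables are my assumptions; hence the range of 81 to 117. The at-least-one percentages also depend on the assumed correlation. That the conflict exists depends on none of these.

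This should be corrected, but it does not threaten the feasibility objective. One complication is that Item 6 lists quadriceps strength and morphology under Primary Outcomes, while Item 4 and Statistical Analyses treat them as secondary. Until that is settled, the loose rule may also reach outcomes labelled primary.

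**What to change.** 1. Delete the trend sentence from the Data Analysis Plan.
2. Amend Statistical Analyses as well, since deletion alone would leave a significance purpose with no level. State that the secondary comparisons are exploratory estimates. For each outcome and contrast, report the number of pairs and the Hodges-Lehmann median change with the 95% confidence interval obtained by inverting the planned Wilcoxon test, and do not describe any result as significant or as a trend. With 20 untied pairs the exact interval has coverage 1 − 0.0484 = 95.2%.
3. State that T0-T2 and T1-T2 include the effect of surgery and are not estimates of the training effect.
4. If one key comparison is wanted, name the outcome, leg, contrast (T0-T1) and two-sided alpha in advance. If it is quadriceps torque, first reconcile its primary or secondary label. Also confirm that strength is measured at Visit 08: the procedures listed there do not include it, although Item 4 expects strength data at T1.
5. Alongside the change values already planned, report the SD of change with its confidence interval for designing the later trial. Do not carry the uncontrolled pre-post change forward as the treatment effect.

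The cost is a wording change, with the same participants, data and software. The downside is fewer positive-sounding statements in the report.
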